PARTNERS HUMAN RESEARCH COMMITTEE PROTOCOL SUMMARY

Answer all questions accurately and completely in order to provide the PHRC with the relevant information to assess the risk-benefit ratio for the study. Do not leave sections blank.

PRINCIPAL/OVERALL INVESTIGATOR

[name]

PROTOCOL TITLE

Muscle synergies during the gait in children with cerebral palsy undergoing robot-assisted gait therapy.

FUNDING

VERSION DATE

Protocol closed on September 8, 2020

Last approval on May 3, 2019

Original approval on October 8, 2015

SPECIFIC AIMS

Concisely state the objectives of the study and the hypothesis being tested.

Aim 1. To study the characteristics of muscle synergies in children with cerebral palsy during gait.
Aim 2. To study the relationship between muscle synergies and the outcomes of robot-assisted gait training.

BACKGROUND AND SIGNIFICANCE

Provide a brief paragraph summarizing prior experience important for understanding the proposed study and procedures.

Cerebral Palsy (CP) is a group of disorders affecting movement, development and posture that cause functional limitation, attributed to non progressive alterations occurring in the brain during fetal and newborn development¹. CP is one of the most common causes of disability in childhood. The prevalence rate of CP is approximately 2/1,000^{2,3}. Clinical features of children with CP usually includes weakness, spasticity, and loss of selective motor control (SMC)⁴. Selective motor control has been defined as 'the ability to isolate the activation of muscles in a selected pattern in response to demands of a voluntary movement or posture'⁴ and the knowledge regarding the etiology of selective motor deficits in children with spastic CP is not well studied yet⁵.

The scientific community widely accepts that the Central Nervous System (CNS) adopts several strategies to reduce the complexity of the control of movement⁶⁻¹⁰. Many authors have shown that one of these strategies consists in using a limited number of primitive signals undergoing the activation of muscles which, when combined, generate a full collection of movements⁹.

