We have observed a significant variability in the clinical outcomes of robot-assisted gait training in children with CP using the Lokomat robotic system. We hypothesize that the severity of impairment in Selective Motor Control (SMC)²¹ is responsible in large part for the variability in responsiveness to robot-assisted gait training observed across children with CP. In the proposed project, we intend to explore the use of a recently developed technique designed to analyze the activity of muscles. This technique is referred to as the “analysis of muscle synergies”. We observe that the study of muscle synergies would allow us to capture the severity of impairments in SMC in a way that is more mechanistic (and therefore more informative) than traditional clinical scales to assess SMC. Furthermore, we hypothesize that abnormalities in muscle synergies would account for the above-mentioned variability in responsiveness to robot-assisted gait training. If this hypothesis was found to be true, the proposed approach would allow us to design patient-specific rehabilitation interventions that would target abnormalities in muscle synergies that could be used prior to the administration of robot-assisted gait training as a way to re-enable motor learning strategies that would allow children with CP who are currently not responsive to robot-assisted gait training to fully benefit from robot-assisted gait training. If successful, the proposed approach would be expected to significantly improve clinical outcomes of robot-assisted gait training in children with CP.

Figure 1. The driven gait orthosis (Lokomat, by Hocoma AG) that we propose to use in the study.

RESEARCH DESIGN AND METHODS

Briefly describe study design and anticipated enrollment, i.e., number of subjects to be enrolled by researchers study-wide and by Partners researchers. Provide a brief summary of the eligibility criteria (for example, age range, gender, medical condition). Include any local site restrictions, for example, “Enrollment at Partners will be limited to adults although the sponsor’s protocol is open to both children and adults.”

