A convenience sample of 30 children with CP with no major orthopedic or neurological complications that could interfere with the gait-training program will be recruited in the study. A study clinician will screen potential subjects. Screening will include a standard history and physical exam to ensure subjects meet all entry requirements after consideration of inclusion and exclusion criteria.

Inclusion criteria:

- Diagnosis of spastic CP
- 6 to 18 years of age.
- Gross Motor Function (GMFCS) Level I, II, III or IV.
- Body/femoral length < size of Lokomat robotic arm (femur length between 210-350mm)
- Ability to communicate pain or discomfort.

Exclusion Criteria:

- Recent use of Lokomat within the last 3 months.
- Contraindication to robot-assisted gait training such as thromboembolic disease, progressive neurologic disorder, cardiovascular or pulmonary contraindications, aggressive behaviors, severe cognitive deficits, bone instabilities, fractures, osteoporosis).
- Skin ulcers in trunk or lower limbs.
- Hip, knee, ankle arthrodesis.

Briefly describe study procedures. Include any local site restrictions, for example, “Subjects enrolled at Partners will not participate in the pharmacokinetic portion of the study.” Describe study endpoints.

All study procedures will take place in the Motion Analysis Laboratory at Spaulding Rehabilitation Hospital, Boston, Massachusetts, USA. Spaulding Rehabilitation Hospital is an affiliated hospital of Harvard Medical School.

Assessments

Assessments will be performed before and after the study participant undergoes robot-assisted gait therapy. Each assessment will require approximately 4-hours. The majority of this time will be spent sitting down, attaching markers and electrodes on the subject, checking the position of the markers and sensors, and measuring lengths of body segments. But we will give the option to the families of dividing the assessments into two different appointments.

Visit 1: Clinical tests

Clinical tests will be conducted by a study staff to assess lower limb function before and after the intervention. Throughout the study visit (notably during the clinical testing) if subjects feel tired, they will be given every opportunity to rest; this, in addition to regular rest breaks between the test trials. Clinical tests will include:

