- The *Gross Motor Function Measure* (GMFM): this standardized test was designed specifically for children with CP and was developed to measure changes over time in clinical status. The GMFM is a classification system based on movements initiated by the child. It can be used to classify the severity of CP related to mobility. For the purpose of this study, the standing and walking sections of the GMFM will be used.
- The *10-meter walk test* will be used to assess walking speed. Subjects will be asked to ambulate at their normal, comfortable walking speed during the test. Individuals using an assistive device during baseline examination will be evaluated with a similar device during subsequent tests. To estimate gait speed, time will be recorded during the middle 10m of the 14m walk test. We may ask subjects to do this test 3-5 times. Each subject will be allowed to rest between trials.
- The *6-minute walk test* will be used to measure walking endurance. The test measures the distance ambulated during 6 minutes of a continuous walk on a flat, uncarpeted surface. An observer walks alongside the subject and provides encouragement and contact guarding as needed. Subjects will be asked to do this test once.

Visit 1: Lab-based study

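### Selective motor control is measured only through gait synergies, an unvalidated proxy, and the SAP plans no synergy–response analysis, so Aim 2 has no analysis and overall severity could explain any association found.

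*Protocol*

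**What the plan says.** The Protocol's Background and Significance section makes three linked statements.

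- A first hypothesis, about SMC. How badly it is impaired, the Protocol says, "is responsible in large part for the variability in responsiveness to robot-assisted gait training observed across children with CP".
- A premise about measurement: synergies would describe that impairment in terms the Protocol calls "more mechanistic (and therefore more informative) than traditional clinical scales to assess SMC".
- A second hypothesis, about synergies: "we hypothesize that abnormalities in muscle synergies would account for the above-mentioned variability in responsiveness to robot-assisted gait training".

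The same section describes the clinical picture: "Clinical features of children with CP usually includes weakness, spasticity, and loss of selective motor control (SMC"). It also states that synergy-based complexity of control is related to functional ability and clinical measures.

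Under Specific Aims, Aim 1 is to characterise synergies during gait and Aim 2 is to relate synergies to training outcomes. Neither mentions SMC or an SMC scale.

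The clinical tests are the GMFM ("For the purpose of this study, the standing and walking sections of the GMFM will be used"), the 10-meter walk test and the 6-minute walk test. The lab study is surface EMG and motion capture during walking. Entry requires GMFCS level I, II, III or IV, and "Screening will include a standard history and physical exam", whose contents are not itemised.

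The SAP adds the Edinburgh Visual Gait Score and the cosine similarity of each child's synergies to normative synergies. Its analysis is descriptive: pre/post comparison, with the mean and standard deviation of each change.

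**The concern.** Two gaps meet here.

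The first is measurement. One hypothesis concerns SMC and the other concerns synergies, but only synergies are measured. With no second measure of SMC, both hypotheses reduce to the same test and the data cannot separate them. The study also cannot show that its synergy measure tracks SMC, or that it does so better than a clinical scale.

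The second is analysis. The SAP contains no correlation, regression or other link between synergies and response. If an association were later reported, nothing in the plan would distinguish a specific effect of synergies from the fact that children with milder or more severe CP may differ in both synergies and response.

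At stake is what the trial may conclude. Without a planned and adjusted analysis, Aim 2 rests on whatever is chosen after the data are seen. A positive result could then be attributed to SMC when the data show, at most, an association with synergies, and perhaps only with severity.

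**Working it through.** The plan gives no figure for this point. Its only design number is a convenience sample of 30, with no alpha, power or effect size. The check therefore compares the text first and then gives illustrations on assumed values.

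**1. What is claimed against what is measured**

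| Item | Where | Measures SMC apart from gait EMG? |
|---|---|---|
| GMFM standing and walking | Protocol, Clinical tests; SAP | No, gross motor function |
| 10-meter walk test | Protocol, Clinical tests; SAP | No, speed |
| 6-minute walk test | Protocol, Clinical tests; SAP | No, endurance |
| Edinburgh Visual Gait Score | SAP | No, visual gait score |
| EMG and motion capture | Protocol, Lab-based study | No, the source of the synergies |
| Synergy cosine similarity | SAP | No, the proxy itself |

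The Background defines SMC as isolating muscle activation to meet the demands of a voluntary movement or posture. EMG is recorded during walking, and no isolated-movement task is listed. That synergies stand for SMC is thus an assumption the study does not check.

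**2. How loosely a proxy result fixes the SMC result (assumed values)**

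Let r be the synergy–response correlation and a the synergy–SMC correlation. The SMC–response correlation must lie within a·r ± √[(1 − a²)(1 − r²)]. With r = 0.5:

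- a = 0.6: 0.30 ± 0.69, or −0.39 to 0.99
- a = 0.8: 0.40 ± 0.52, or −0.12 to 0.92
- a = 0.9: 0.45 ± 0.38, or 0.07 to 0.83

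These are mathematical limits, not likely values. An imperfect clinical SMC scale would be subject to the same formula.

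**3. How much severity could explain (assumed values)**

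Let severity correlate c with synergies and also c with response, and keep r = 0.5. The synergy–response correlation adjusted for severity is (r − c²)/(1 − c²).

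- c = 0.3: (0.5 − 0.09)/0.91 = 0.45
- c = 0.5: (0.5 − 0.25)/0.75 = 0.33
- c = 0.7: (0.5 − 0.49)/0.51 = 0.02

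The documents do not give c. The same unadjusted 0.5 could be mostly a synergy effect or almost wholly a severity effect.

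**4. What 30 children can show**

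At two-sided alpha 0.05 and 80% power (both assumed), the smallest detectable correlation is tanh[(1.96 + 0.84)/√(n − 3)]: 0.49 at n = 30, 0.54 at n = 25 and 0.59 at n = 20.

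For an observed 0.5 at n = 30, the Fisher 95% interval is tanh(0.549 ± 1.96/√27), or 0.17 to 0.73. For a partial correlation of 0.5 with two covariates, √27 becomes √25 and the interval is 0.16 to 0.74. The degrees of freedom cost little. The slope's standard error also rises by about 1/√(1 − c²) from overlap between severity and synergies: 1.15-fold at c = 0.5 and 1.40-fold at c = 0.7, before any residual variance that the covariates remove.

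**5. What adding an SMC scale would have bought**

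For two dependent correlations with response at n = 30, the Meng–Rosenthal–Rubin test has about 17% to 32% power for 0.5 against 0.3, and 35% to 64% for 0.6 against 0.3. The ranges cover synergy–scale correlations of 0.3 to 0.7, all assumed. A scale would make the comparison possible, but not well powered in these scenarios.

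**The case against.** The strongest reply is that the study does not need an SMC scale. Both aims are about synergies. The second hypothesis is about synergies, and the targeted interventions the Background hopes for follow from that hypothesis and are aimed at synergy abnormalities. The comparison with SMC scales is introduced as an observation, so it is rationale and not a hypothesis under test. All of this stands.

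A reader might infer that neither SMC statement can be tested, or that a missing scale defeats the study's purpose. The documents do not support that. The Protocol names synergies as its measure of SMC severity, so the SMC hypothesis can be examined indirectly. Only the comparative premise is wholly out of reach. Aim 2 lacks an analysis, not a scale.

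A reader might also take the bounds in step 2 to show that the SMC–response relation is almost undetermined here. They rest on assumed inputs and extreme cases, and at a = 0.9 they exclude zero.

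Three further limits apply. The list of clinical tests may not be exhaustive, since the SAP adds a scale absent from it, and part of the SAP was not in the text available. The physical exam might record weakness, spasticity or SMC, but the documents do not say. And the Protocol is recorded as closed on September 8, 2020, so a baseline scale is not a practical remedy for children already enrolled.

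None of this supplies the missing synergy–response analysis or removes severity as a competing explanation.

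**Conclusion.** The concern holds in a limited form. On the available text, no measure of SMC independent of gait synergies is collected. The SMC hypothesis is therefore examinable only through a proxy that the study does not validate, and the premise that synergies outperform clinical SMC scales is untestable.

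The more consequential part is that the SAP plans no synergy–response analysis. Aim 2 has none, and any association reported later would be open to explanation by overall severity.

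The size of that confounding cannot be taken from the documents. Under the assumed correlations above, an unadjusted 0.5 corresponds to an adjusted value between 0.45 and 0.02. The conclusion itself rests on the listed measures, the eligible GMFCS range and the Background's own link between synergies and function, not on those illustrative figures.

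**What to change.** 1. **Specify the Aim 2 analysis in the SAP.** For each outcome, regress the change on baseline synergy cosine similarity, first alone and then with baseline GMFM and GMFCS level. Enter GMFCS as one ordinal term and baseline GMFM as one score. State how similarity is reduced to one value per child. Report the synergy estimate and its 95% confidence interval from both models, and describe the second as what synergies add beyond severity.
2. **Limit the conclusion.** Word the findings in terms of synergies. Drop the attribution to SMC and the claim of being more informative than clinical SMC scales, unless an SMC scale was in fact scored.

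Baseline GMFM is a listed test. GMFCS level is needed for eligibility, so it should be available, but confirm that it was recorded as data.

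The cost is SAP and reporting text, one or two degrees of freedom at n = 30, some loss of precision if synergies and severity overlap strongly, and a narrower conclusion. No visit or assessment is added. The adjusted analysis addresses confounding by severity only. Neither GMFM nor GMFCS scores SMC, so it must not be presented as a test of synergies against SMC scales.

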supported by an unloading system. The DGO is meant to replace the assistance provided by therapists during manually-assisted treadmill-based gait training. The DGO records parameters such as the joint torques, the range of motion at different joints and the level of assistance provided by the robot. These parameters allow therapists to monitor the subject’s response to gait training. The Pediatric Lokomat is a DGO for gait training in children. Its safety and benefits on speed, gait endurance, gross motor skills (assessed using the Gross Motor Function Measure Scale)^{16,18}, postural control¹⁹, hip extension, step length²⁰ and spasticity have already been demonstrated in many studies. Some of these intervention outcomes have been shown to be retained 6 months post-therapy²⁰. In comparison to conventional therapy and manually assisted body weight-supported treadmill training, robot-assisted gait training allows for significantly increasing the number of steps performed during a single session. Besides, the system can assure the performance of a physiological pattern of motion during training. Given its benefits, DGOs like the Lokomat system are becoming more and more common in clinical practice.

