6. Patients with CP who previously volunteered to be contacted about opportunities to participate in research studies at Spaulding Rehabilitation.
7. Contact with patients who received robot-assisted gait training as part of the clinical program at Spaulding Rehabilitation Hospital via referrals from physical therapists.
8. Via advertisement on clinicaltrials.partners.org and researchmatch.org websites.
9. Via letter to prospective subjects co-signed by their physician and study PI.
10. Via contact to the patients listed for direct contact in the Partners Research Patient Data Registry (RPDR).

Provide details of remuneration, when applicable. Even when subjects may derive medical benefit from participation, it is often the case that extra hospital visits, meals at the hospital, parking fees or other inconveniences will result in additional out-of-pocket expenses related to study participation. Investigators may wish to consider providing reimbursement for such expenses when funding is available

Subjects will be compensated based on the procedures undertaken. The compensation amount will be as follows:

- \$35 for evaluation sessions
- \$15 for intervention sessions

For guidance, refer to the following Partners policies:

Recruitment of Research Subjects

<http://healthcare.partners.org/phsirb/recruit.htm>

Guidelines for Advertisements for Recruiting Subjects

<http://healthcare.partners.org/phsirb/advert.htm>

Remuneration for Research Subjects

<http://healthcare.partners.org/phsirb/remun.htm>

CONSENT PROCEDURES

Explain in detail how, when, where, and by whom consent is obtained, and the timing of consent (i.e., how long subjects will be given to consider participation). For most studies involving more than minimal risk and all studies involving investigational drugs/devices, a licensed physician investigator must obtain informed consent. When subjects are to be enrolled from among the investigators' own patients, describe how the potential for coercion will be avoided.

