**NCT06156969**

**MAY 3RD, 2019**

## DATA ANALYSIS PLAN

Descriptive statistics will be derived for the primary and secondary outcome measures used in the study. Outcome measure values will be compared pre- vs post-intervention to assess changes associated with robot-assisted training. Cosine similarity values will be derived by comparing the composition of the muscle synergies pre- and post-intervention with normative synergies. The difference between post- and pre-intervention cosine similarity values will be measured as percentage of the scale (0-1 value). Data for the Gross Motor Function Measure scale section D and E will be compared pre- vs post-intervention, and the difference will be measured as percentage of the scale range (i.e. 39 points for the section D score and 72 points for the section E score). Finally for the 10-meter walk test, the 6-minute walk test and the Edinburgh Visual Gait Score scale, we will estimate the improvement in clinical outcome measure and derive the percentage improvement relative to the baseline value. For each of these outcome measures, we will estimate mean and standard deviation values of the improvement in clinical score for each outcome measure as explained above.

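### Does the plan need a prior-Lokomat variable because previously trained children can enter the study?

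*Protocol*

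**What the plan says.** The protocol (Research Design and Methods, Exclusion Criteria) lists "Recent use of Lokomat within the last 3 months". Older use is not excluded. Recruitment Procedures, source 7 of ten, is "Contact with patients who received robot-assisted gait training as part of the clinical program at Spaulding Rehabilitation Hospital".

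Background and Significance states that "Some of these intervention outcomes have been shown to be retained 6 months post-therapy". The reference attached to that statement is the one attached, in the sentence before it, to "hip extension, step length".

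Aim 2 is "To study the relationship between muscle synergies and the outcomes of robot-assisted gait training".

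The SAP (Data Analysis Plan) states: "Outcome measure values will be compared pre- vs post-intervention to assess changes associated with robot-assisted training". GMFM sections D and E and cosine similarity are expressed as a percentage of a fixed scale. For the 10-meter walk, the 6-minute walk and the Edinburgh score the plan is to "derive the percentage improvement relative to the baseline value". Each outcome gets one mean and SD of improvement. No subgroup, covariate or prior-exposure variable is named.

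**The concern.** Read together, these statements suggest an uncontrolled influence. The exclusion window is 3 months, the protocol cites retention at 6 months, and the site recruits from its own former robot-training patients. A child trained four or five months earlier could enter with gains still present.

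Two things would be at stake. First, the single mean change would average over trained and untrained children, and a reader could not tell to whom it applies. Second, the protocol hypothesises that abnormal synergies explain who responds. If earlier training changed both the baseline synergies and the remaining room to improve, it would be a rival explanation for any association found under Aim 2. With one group and no control, readers have few other safeguards.

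**Working it through.** The plan has no figure to reproduce: the 30 children are a convenience sample, with no stated effect size, SD or power. The documents do not give the share previously trained or the effect of that training, so those inputs are assumptions.

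**1. Is the pre/post change biased?** Let a child's level be Y, the retained earlier gain R and the new gain G. The absolute change is (Y + R + G) − (Y + R) = G. A stable retained gain drops out. The fixed-scale outcomes (GMFM D and E, cosine similarity) are unaffected if gains add. If gains do not add, the mean still describes the children enrolled. It differs only from what untrained children would show, and neither document makes them the target.

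**2. How far could the mean sit from an untrained-only mean?** Assume a share p of 0.10 to 0.30 (3 to 9 of 30).

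- Fixed-scale outcomes, shift = p × (relative gain − 1). Half the gain: −5% to −15% of the mean improvement. Equal gain: 0. A gain 1.25 times as large: +2.5% to +7.5%.
- Percent-of-baseline outcomes where higher is better, gains adding and an earlier gain g fully kept, shift = p × (1/(1 + g) − 1). g = 0.1: −0.9% to −2.7%. g = 0.2: −1.7% to −5.0%.
- Where lower is better, shift = p × (1/(1 − g) − 1). g = 0.1: +1.1% to +3.3%. g = 0.2: +2.5% to +7.5%. The documents do not give the Edinburgh score's direction, nor say whether the 10-meter test is analysed as time or speed, so the sign for those two is open.

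In SD units, a difference of s = 0.5 to 1 SD moves the mean by p × s = 0.05 to 0.30 SD. The 95% half-width for a mean change at n = 30 is t(0.975, 29)/√30 = 0.373 SD.

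**3. Aim 2.** Suppose earlier training shifts both the synergy score and the response by d within-group SDs. With v = p(1 − p), the correlation it creates is v·d²/(1 + v·d²).

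| p | d = 0.5 | d = 1 |
|---|---|---|
| 0.1 | 0.022 | 0.083 |
| 0.2 | 0.038 | 0.138 |
| 0.3 | 0.050 | 0.174 |

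The correlation needed for two-sided 5% significance at n = 30 is t/√(t² + 28) with t = 2.048, which is 0.361. The largest entry is under half of that.

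**4. What would an added analysis show?** The half-width of a trained-versus-untrained difference is t(0.975, 28) × √(1/n₁ + 1/n₂):

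- 3 v 27: 1.25 SD
- 6 v 24: 0.93 SD
- 9 v 21: 0.82 SD

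Leaving out 3, 6 or 9 children raises the half-width of the mean change from 0.373 to 0.396, 0.422 or 0.455 SD, that is 6%, 13% or 22% wider. Restricting at 6 months, the only retention time cited, would still leave in children trained longer ago, so it would not isolate an untrained group.

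**The case for a change.** The best argument for a change is that previously trained children are a named recruitment stream, and that the protocol's own 3-month exclusion treats prior exposure as relevant. The protocol also credits Lokomat training with benefits on speed, endurance and gross motor skills, which this study measures. Two data items and a table cost little. The ranges above can also be pushed: with half the sample trained and a 1 SD difference, the mean would sit 0.5 × 1 = 0.50 SD from the untrained value, more than the 0.373 SD half-width.

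Part of this stands. A mixed sample is possible, the plan does not describe it, and prior training is a plausible confounder of a synergy-response relation. The rest does not carry a change. The 0.50 SD is a distance from a population the study does not claim to estimate, and nothing supports a share that high. Even there the Aim 2 correlation would be 0.25/1.25 = 0.20, still below 0.361. The 6-month retention reference is the one given for hip extension and step length, which the SAP does not list, so retention on this study's endpoints is not shown. GMFCS levels I to IV and ages 6 to 18 are also mixed without being analysis variables, and nothing shows that earlier Lokomat use matters more. Finally, the Data Analysis Plan sets out no analysis relating synergies to outcomes. That is the larger gap for Aim 2, and a prior-exposure variable has no planned model to enter.

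**Conclusion.** No change to the plan follows. As written, it gives a sound pre/post description of the children enrolled. Earlier Lokomat training is possible effect modification within that group, not a demonstrated bias. Under assumed shares of 10% to 30% and shifts of 0.5 to 1 SD, the mean would lie at most 0.30 SD from an untrained-only value, and the induced Aim 2 correlation at most about 0.17; both are inside the sampling error at n = 30. A breakdown by exposure would be too imprecise to resolve the matter, and a restricted analysis would cost precision without isolating untrained children.

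What remains is a reporting detail. Applying the 3-month exclusion already requires asking about Lokomat use at screening, so the number of children with earlier training can be given with the baseline characteristics where records allow. The conclusion rests on the assumed shares and shifts and on the enrolled children being the target. It would need another look if records showed that a large majority had been trained before, or if the results were presented as applying to Lokomat-untrained children.
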